To compare the effect of selumetinib relative to placebo by assessment of chronic target PN pain palliation and time to chronic target PN pain palliation in patients with a PAINS-pNF chronic target PN pain score of ≥ 3 at baseline.					
Secondary	Proportion of patients with chronic target PN pain palliation during the randomised period	Subset of the Pain FAS with an evaluable baseline assessment and at least one evaluable post-baseline assessment	Post randomised study intervention discontinuation: while on-treatment strategy; study intervention interruption greater than 28 days: while on-treatment strategy; change in (chronic PN) pain medication: composite strategy; early crossover due to documented progression on imaging: while on-treatment strategy; target PN resection: treatment policy strategy	Odds ratio between selumetinib and placebo in proportion of patients with chronic target PN pain palliation using random-effect logistic regression with geographical region, treatment and cycle as a factors and covariates including baseline PAINS-pNF pain intensity score and baseline pain medication score	4.2.9

Secondary	Time to chronic target PN pain palliation	Subset of the Pain FAS with an evaluable baseline assessment and at least one evaluable post-baseline assessment	Post randomised study intervention discontinuation: while on-treatment strategy; study intervention interruption greater than 28 days: while on-treatment strategy; change in pain medication: composite strategy; early crossover due to documented progression on imaging: while on-treatment strategy; target PN resection: treatment policy strategy	KM method, stratified log-rank test, Cox proportional hazards model adjusted for treatment and geographical region as fixed effects and baseline chronic target PN pain intensity score and baseline chronic PN pain medication modified WHO analgesic ladder score as covariates	4.2.10
-----------	---	--	--	---	------------------------

To compare the effect of selumetinib relative to placebo by assessment of pain medication compared with baseline.

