4.2.2.1.5 Primary Analysis of the 1st Key Secondary Endpoint

The difference in the mean change from baseline in PAINS-pNF chronic target PN pain score at Cycle 12 between treatment groups (selumetinib minus placebo), standard error, 95% CI and p-value will be assessed by least-squares (LS) means of a MMRM with randomised study intervention, cycle number, and geographical region as categorical fixed effects; the baseline PAINS-pNF chronic target PN pain intensity score as a continuous covariate; and treatment-by-cycle number and baseline PAINS-pNF score-by-cycle number interactions. Parameters will be estimated with the restricted maximum likelihood (REML) approach ([Brown and Prescott 2006](#)), and the Kenward-Roger approximation is used to estimate the degrees of freedom.

The analysis will include PAIN-FAS patients with at least one post-baseline average cycle PAINS-pNF chronic target PN pain intensity score. Data obtained during the randomised period (see Section 3.3.2.2) will be included in the analysis, and the intercurrent event strategy is described in, Section 4.2.2.1.4.

The analysis will be conducted using PROC MIXED in SAS.

Missing PAINS-pNF chronic target PN pain intensity scores will be modelled through direct likelihood techniques, which use the information from the observed pain intensity scores via the within-patient correlation structure (covariance matrix) to provide information about the unobserved pain intensity scores. Random (subject-specific) effects will be not explicitly modelled, and an unstructured covariance matrix will be used to

model the within-patient correlations between the repeated measurements and to allow for unequal treatment variance.

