An unstructured modelling of within-patient correlations removes one layer of assumptions on the random effects and often provides the best fit to the data. In case of missing data, the use of an unstructured covariance matrix in the MMRM can guarantee a more robust control of type I error by better detecting even small treatment differences compared with the single imputation methods such as last observation carried forward, even in case of unequally distributed dropout rates across treatment arms and regardless of the form of the true covariance matrix (Mallinckrodt et al 2008). If the fit of the unstructured covariance structure fails to converge, every attempt should be made to ensure convergence is obtained from the unstructured correlation structure. Parameters will be tried to be estimated by means of the Fisher's scoring algorithm rather than the default Newton-Raphson algorithm.

If convergence is still not reached after the change in the interaction algorithm, a more parsimonious model will be implemented using one of the following structured covariance structures in order until convergence is reached: toeplitz with heterogeneity, autoregressive with heterogeneity, toeplitz, autoregressive, and compound symmetry. All main effects and the interaction terms will remain in the model, regardless of significance.

In addition to the Cycle 12 estimate, the model will present LS mean estimates for each treatment group and their differences, standard errors, 95% CIs, and p-values (where applicable and with statistical significance effects being interpreted as nominally significant) for mean changes from baseline to each cycle during the randomised period (based on the treatment-by-cycle interaction coefficient) and the average over the randomised period (based on the treatment coefficient). A plot of the LS means accompanied by the 95% CI will be produced. Variables listed as categorical in the list above will be included in the CLASS statement of the procedure. The unique patient identifier will also be included as a class variable. A REPEATED statement over the visits will be included with the unique patient identifier as the SUBJECT variable in the REPEATED statement.

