4.2.2.5 Primary Analysis of the 2nd Key Secondary Endpoint

The difference in the mean change from baseline in PlexiQoL total score at Cycle 12 between treatment groups (selumetinib minus placebo), standard error, 95% CI, and p-value will be assessed by LS means of an MMRM with randomised study intervention, cycle number, geographical region and average baseline chronic target PN pain intensity group as categorical fixed effects; the baseline PlexiQoL total score as a continuous covariate; and treatment-by-cycle number and baseline PlexiQoL total score-by-cycle number interactions. Parameters will be estimated with the REML approach, and the Kenward-Roger approximation is used to estimate the degrees of freedom.

The analysis will be performed on a subset of the FAS population with an evaluable baseline assessment and at least one evaluable post-baseline assessment. Evaluable assessment is defined as a PlexiQOL total score. Data collected during the randomised period (see Section 3.3.2.2) will be included, adhering to the intercurrent event strategy (refer to Section 4.2.2.2.3).

The analysis will be conducted using PROC MIXED in SAS using the same model specifications as specified for the 1st key secondary endpoint (see Section 4.2.2.1.5). All main effects and the interaction terms will remain in the model, regardless of significance.

In addition to the Cycle 12 estimate, the model will present LS mean estimates for each treatment group and their differences, standard errors, 95% CIs, and p-values (where applicable and with statistical significance effects being interpreted as nominally significant) for mean changes from baseline to each cycle during the randomised period (based on the treatment-by-cycle interaction coefficient) and the average over the randomised period (based on the treatment coefficient). A plot of the LS means accompanied by the 95% CI will be produced.

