4.2.9.5 Primary Analysis of Chronic Target PN Pain Palliation

The pain palliation response during the randomised period is analysed using a random-effect logistic regression model including treatment, geographical region, and cycle number as fixed effects; baseline chronic target PN pain intensity score and baseline

chronic PN pain medication modified WHO analgesic ladder score as covariates; and the following interaction terms: treatment-by-cycle number, baseline chronic target PN pain intensity score-by-cycle number, and baseline chronic PN pain medication score-by-cycle number.

The analysis will be conducted using PROC GLIMMIX in SAS with a random intercept also included to account for variability between patients. Random (subject-specific) effects will be not explicitly modelled, and an unstructured covariance matrix will be used to model the within-patient correlations between the repeated measurements and to allow for unequal treatment variance. An unstructured modelling of within-patient correlations removes one layer of assumptions on the random effects and often provides the best fit to the data.

If the fit of the unstructured covariance structure fails to converge, every attempt should be made to ensure that convergence is obtained from the unstructured correlation structure. Parameters will be tried to be estimated by means of the Fisher's scoring algorithm rather than the default Newton-Raphson algorithm. If convergence is still not reached after the change in the interaction algorithm, a more parsimonious model will be implemented using one of the following covariance structures in order until convergence is reached: toeplitz with heterogeneity, autoregressive with heterogeneity, toeplitz, autoregressive, and compound symmetry. All main effects and the interaction terms will remain in the model, regardless of significance.

The results of the analysis are presented in terms of an odds ratio (selumetinib versus placebo) together with its 95% CI and p-value at each cycle of the randomised period (estimated using the treatment-by-cycle interaction coefficient) and overall, over the randomised period (based on the treatment coefficient). For each treatment arm, the odds will be presented along with the number of non-missing observations used in the estimation (n), the observed number and percentage of responder, and the corresponding 95% CI.

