4.2.11.5 Primary Analysis of Pain Medication

The pain medication decrease during the randomised period will be analysed using a random-effect logistic regression model including treatment, geographical region, and cycle number as fixed effects; baseline chronic PN pain medication score as covariates; and the following interaction terms: treatment-by-cycle number and baseline chronic PN pain medication score-by-cycle number.

A random intercept will also be included to account for variability between patients. An unstructured covariance matrix will be used to allow for unequal treatment variance and to model the correlation between different treatment measurements within the same subject. If the fit of the unstructured covariance structure fails to converge, the following covariance structures will be used in order until convergence is reached: toeplitz with heterogeneity, autoregressive with heterogeneity, toeplitz, autoregressive, and compound symmetry. All main effects and the interaction terms will remain in the model regardless of significance.

The results of the analysis are presented in terms of an odds ratio (selumetinib versus placebo) together with its 95% CI and p-value at each cycle (estimated using the treatment-by-cycle interaction coefficient) and overall, over the randomised period (based on the treatment coefficient). For each treatment arm, the odds will be presented along with the number of non-missing observations used in the estimation (n), the observed number and percentage of responders, and the corresponding 95% CIs. The analysis will be performed on a subset of the FAS population with an evaluable baseline and at least one post-baseline chronic PN pain medication score available. Data collected during the randomised period (see Section 3.3.2.2) adhering to the intercurrent event strategy (refer to Section 4.2.11.3) are included.

This analysis will be repeated using the sensitivity definition outlined in Section 4.2.11.2. For the sensitivity using investigator assessment of analgesic use, the random-effect logistic regression model will include treatment, geographical region, and cycle number as fixed effects; baseline chronic PN pain medication score as covariate; and the following interaction terms: treatment-by-cycle number and baseline chronic target PN pain medication score-by-cycle number.

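### Chronic target PN pain palliation (SAP 4.2.9.5): the model both includes and disclaims a random intercept, the odds ratios are tied to single coefficients, and the protocol's difference in proportions is not a planned output

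*SAP*

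**What the plan says.** **Model.** SAP 4.2.9.5 analyses palliation (yes or no at each cycle) with a logistic model that it labels random-effect, fitted in PROC GLIMMIX "with a random intercept also included to account for variability between patients. Random (subject-specific) effects will be not explicitly modelled". That second sentence continues with an unstructured matrix for the within-patient correlations, and a fallback list of simpler structures follows. The endpoint table in SAP 4.2 gives the summary measure as "Odds ratio between selumetinib and placebo in proportion of patients with chronic target PN pain palliation using random-effect logistic regression".

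Nearly the same disclaimer stands in SAP 4.2.2.1.5, the PROC MIXED analysis of pain intensity: "Random (subject-specific) effects will be not explicitly modelled, and an unstructured covariance matrix will be used to" model the within-patient correlations. That model has no random intercept, so the sentence is coherent there. The sister analysis of pain medication decrease (SAP 4.2.11.5) specifies a random intercept and an unstructured matrix together, without the disclaimer.

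**Reported effect.** In 4.2.9.5 the odds ratio at each cycle is "estimated using the treatment-by-cycle interaction coefficient) and overall, over the randomised period (based on the treatment coefficient"). All interaction terms stay in the model whatever their significance. SAP 4.2.11.5 uses the same rule: "p-value at each cycle (estimated using the treatment-by-cycle interaction coefficient) and overall". The primary analysis of the second key secondary endpoint has similar wording, "based on the treatment-by-cycle interaction coefficient) and the average over the randomised period (based on the treatment coefficient"), but there and in 4.2.2.1.5 it is attached to LS means: "the model will present LS mean estimates for each treatment group and their differences". For each arm, 4.2.9.5 prints the odds, the number of observations, "the observed number and percentage of responder, and the corresponding 95% CI".

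**Protocol measure.** Protocol 1.1 (objectives table), Section 3 (Table 4) and Section 9.4.2.3.7 all state the effect as a difference between arms in the proportion of participants with palliation, by cycle and over the whole randomised period. Section 9.4.2.3.7 leaves the full analysis detail to the SAP. SAP Section 2 lists five changes to the protocol's analyses; none concerns palliation.

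**The concern.** For a continuous outcome, the choice between a random intercept and a structured within-patient covariance does not change what the treatment effect means. On the logit scale it does. A model with a random intercept estimates an odds ratio for a given patient. A model with only a within-patient covariance estimates an odds ratio that is not conditional on the patient, though still adjusted for the fixed covariates. SAP 4.2.9.5 asks for both and does not say which is reported, so two programmers could follow it faithfully and deliver different quantities from the same data. The section also repeats the analysis under its sensitivity definitions, so the ambiguity carries over to them.

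A reader who took a patient-conditional odds ratio for the other kind would overstate the difference in proportions. That difference is the measure the protocol names, and no between-arm estimate of it with a confidence interval is planned that would correct the reading.

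**Working it through.** The documents give no sample size, palliation rate or between-patient SD for this endpoint, so there is no plan figure to reproduce. All rates, odds ratios and SDs below are assumptions.

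**1. Effect of the random intercept.** Take marginal rates of 30% and 15%.
- Without the intercept: (0.30/0.70) / (0.15/0.85) = 0.4286 / 0.1765 = 2.43.
- With a normal intercept of SD s, solve for the linear predictor in each arm so that the rate averaged over the intercept equals 30% or 15% (Gauss-Hermite quadrature). The conditional odds ratio is the exponential of the difference between the two predictors.

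| Rates | No intercept | SD 1 | SD 2 | SD 3 |
|---|---|---|---|---|
| 30% vs 15% | 2.43 | 2.80 | 3.93 | 5.98 |
| 40% vs 25% | 2.00 | 2.28 | 3.05 | 4.33 |
| 50% vs 35% | 1.86 | 2.11 | 2.76 | 3.82 |

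Every row describes the same 15-point difference. These values assume an exact-likelihood fit. The SAP names no estimation method, and PROC GLIMMIX can fit by pseudo-likelihood, which pulls binary-data estimates toward the null. Simulated for 30% vs 15% with 12 cycles and no other covariates, it gave between 2.5 and 2.7 at SD 1, a little over 3 at SD 2 and about 3.5 at SD 3.

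**2. Consequence of misreading.** Treat the conditional odds ratio as if it were not conditional, at a 15% placebo rate: p1 = OR × 0.1765 / (1 + OR × 0.1765), minus 0.15. With the unrounded odds ratios of the first row this gives 18.1, 25.9 and 36.3 points at SD 1, 2 and 3, instead of 15.0.

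**3. Coefficients against contrasts.** With reference coding and a treatment-by-cycle interaction, the treatment coefficient is the log odds ratio at the reference cycle, and each interaction coefficient is the departure from it.
- Constant odds ratio of 2: every interaction coefficient is 0, so the literal per-cycle value is 1.00.
- Odds ratio rising log-linearly from 1 at Cycle 1 to 3 at Cycle 12: at Cycle 6 the log odds ratio is (5/11) × ln 3 = 0.499, an odds ratio of 1.65. With Cycle 12 as reference, the literal Cycle 6 value is exp(0.499 − 1.099) = 0.55.
- In the same case the literal overall value is 3.00 with Cycle 12 as reference, or 1.00 with Cycle 1. The equally weighted average is exp(ln 3 / 2) = 1.73.

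**4. Odds ratio against difference.** An odds ratio of 2.0 implies p1 = 2 × odds0 / (1 + 2 × odds0), where odds0 is the placebo odds. At placebo rates of 10%, 25% and 40% the difference is 8.2, 15.0 and 17.1 points. The crude single-cycle 95% half-width, 1.96 × √[(p1(1 − p1) + p0(1 − p0))/n], is 13.2, 17.6 and 18.7 points with the 53 per arm to be randomised in the pain stratum (106 in total), and 14.8, 19.8 and 21.1 with the 42 per arm required for the pain-intensity endpoint.

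**The case against.** **The intended model is clear enough.** The random-effect label recurs in the SAP 4.2 table, in 4.2.9.5 and in 4.2.11.5, so the disclaimer looks like text carried over from the pain-intensity MMRM. That is probably how it arose. It does not settle the model, because 4.2.11.5 shows that the SAP elsewhere intends a random intercept together with an unstructured matrix.

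**The gap is exaggerated.** A reader might infer that the reported odds ratio will be up to two and a half times another valid one (5.98 / 2.43 = 2.46). The documents do not support that as an expectation: SD 3 is an assumption, and pseudo-likelihood gives less. The direction stands, because with any between-patient variance and a real effect the conditional odds ratio lies further from 1.

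**Per-arm odds would reveal the model.** A reader might also infer that comparing the printed odds with the observed percentages shows which model was fitted. It does not. The model contains region and baseline covariates, so odds at average covariates need not match the raw percentages even without a random intercept.

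**The coefficient wording is shorthand.** Likely so: both sections name an odds ratio of selumetinib against placebo as the target, and the MMRM sections attach the same phrases to LS-mean differences. What stands is that the logistic sections lack that anchor and state no weights for the overall estimate.

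**The protocol defers to the SAP.** It does, and the per-arm percentages allow a crude difference by subtraction. That gives no interval for the difference and no defined overall value, and replacing the stated measure goes beyond added detail.

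**Conclusion.** The point holds as a contradictory and incomplete specification of one secondary analysis. SAP 4.2.9.5 admits three covariance models that do not share one meaning for the odds ratio. Under the assumptions shown, an exact-likelihood conditional odds ratio is 2.80 to 5.98 where the model without the intercept gives 2.43; the true gap depends on the between-patient SD and the estimation method, neither of which is given. The protocol's difference in proportions is not a planned output with an interval, and SAP Section 2 does not record the change. The coefficient wording carries less weight: it is wrong only if taken literally.

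A reader might infer that confirmatory conclusions are at risk. They are not. SAP 3.3.7 limits the multiple testing procedure to ORR, pain intensity and PlexiQoL, and the two MMRM analyses attach the coefficient phrases to LS-mean differences.

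**What to change.** (a) In SAP 4.2.9.5 keep the random-intercept logistic model. Delete the disclaimer, the unstructured-matrix text and its fallback list. Name a likelihood-based method (adaptive quadrature or Laplace), in line with the direct-likelihood handling in SAP Table 15, and state that the odds ratio is conditional on the patient. Use the same covariance specification in 4.2.11.5, or say why it differs.

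(b) In both sections define each cycle's odds ratio as the treatment contrast at that cycle (treatment plus interaction), and the overall one as the average of these log odds ratios with stated weights, for example equal.

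(c) For palliation add the between-arm difference in proportions with 95% CI, standardised from the model, at each cycle and averaged over cycles. If the odds ratio stays the main measure, list that in SAP Section 2.

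The cost is SAP wording and one extra output whose interval needs a delta-method or bootstrap step; no new data are needed. A single random intercept assumes equal correlation between all cycles on the logit scale, which an unstructured matrix would not. That matrix has 12 × 13 / 2 = 78 parameters for 12 cycles, which is a lot for a binary outcome in about 106 patients.

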4.2.10 Time to Chronic Target PN Pain Palliation During the Randomised Period

4.2.10.1 Definition

Time to chronic target PN pain palliation (TTPP) is defined as time to first chronic target PN pain palliation.

The date of the last day of the cycle will be used for calculating the time to event; therefore, time to event will be measured in months. TTPP will be defined as the duration of time in months from randomisation to the date of the last day of the first cycle where chronic target PN pain palliation is achieved.

Chronic target PN pain palliation is defined in Section [4.2.9.1](#).

The main definitions for chronic target PN pain palliation are proposed to be the primary, sensitivity 1, and sensitivity 2 definitions, resulting in 3 time-to-event endpoints. However, other definitions in [Table 14](#) might be considered, especially should the psychometric analysis demonstrate a clinically meaningful within-patient change different than the pre-specified value of 2.

The randomised period is defined in Section [3.3.2.2](#).

